STUDY PROTOCOL

Study name:	Effectiveness of enhanced recovery after surgery (ERAS) protocols for arthroscopic anterior cruciate ligament reconstruction in an ambulatory surgery setting
Duration:	April 16 th 2026 - April 16 th 2027

1. Study Description (Brief summary)

The anterior cruciate ligament (ACL) is a critical component for maintaining knee stability by resisting anterior tibial translation and internal rotation. ACL rupture is one of the most common orthopedic injuries, with an estimated incidence of 70 cases per 100,000 people annually [1]. Since its inception, arthroscopic anterior cruciate ligament reconstruction (AACLRL) has proven to be the gold standard, providing excellent outcomes in terms of graft longevity, return to sports, and patient satisfaction [2]. Modern medical trends are shifting toward day-surgery protocols, where patients are discharged within 24 hours without an overnight stay. This model is identified as a major factor in enhancing the quality of postoperative recovery and patient satisfaction [3].

The Enhanced Recovery After Surgery (ERAS) program utilizes evidence-based multimodal interventions to reduce surgical stress and accelerate functional recovery. While day-surgery for AACLRL has been proven feasible globally, its implementation in Vietnam remains limited due to systemic barriers [4,5]. At the University Medical Center Ho Chi Minh City, although ERAS has been applied since 2022, the average length of stay for AACLRL is 2.57 days, indicating significant room for optimization. This study aims to evaluate the current compliance with ERAS and the effectiveness of fully implementing these protocols to enable a day-surgery model.

The research is designed in two phases, including a descriptive cohort and a clinical intervention. The intervention focuses on 06 core ERAS measures:

- Comprehensive preoperative counseling and education.
- Reducing preoperative fasting by using Maltodextrin 2 hours before surgery.
- Standardized anesthesia combined with local infiltration analgesia (LIA).
- Multimodal analgesia to minimize opioid consumption.
- Early drainage removal within 6–8 hours postoperatively.
- Immediate postoperative rehabilitation starting in the recovery unit.

Effectiveness will be measured through various outcomes: the quality of early recovery via the QoR-15 score, mechanical knee function via the Lysholm Knee Scoring Scale (LKSS), and health-related quality of life via the EQ-5D-5L. Furthermore, a cost-effectiveness analysis (CEA) will be conducted using the Incremental Cost-Effectiveness Ratio (ICER). The study expects to demonstrate that strict ERAS adherence makes day-surgery ACLR feasible, reduces hospital-acquired infections, optimizes operating room productivity, and lessens the financial burden on both patients and the healthcare system.

2. Objective

- 2.1. To describe the current status of ERAS program implementation among patients undergoing arthroscopic anterior cruciate ligament reconstruction (ACLR) at University Medical Center Ho Chi Minh City.
- 2.2. To evaluate the impact of ERAS interventions on postoperative recovery quality, cost-effectiveness, and the feasibility of implementing a day-surgery protocol for patients undergoing ACLR.

3. Materials and methods

Study design: Two-phase study

- Phase 1: Cross-sectional study, Retrospective cohort study.
- Phase 2: Interventional study.

Observational Model: Cohort

Actual study start date: April 16th, 2026

Actual study completion date: April 16th, 2027

4. Criteria

Inclusion criteria

- Patients aged 18 years and older.
- Diagnosis of anterior cruciate ligament (ACL) rupture with indication for primary arthroscopic reconstruction.
- Voluntary agreement to participate in the study and signing of the informed consent form.

Exclusion criteria

- Patients with concomitant knee pathologies requiring additional surgical procedures in the same session.
- Presence of contraindications for ambulatory (day) surgery.
- Failure to adhere to the scheduled follow-up visits.

- Incomplete medical records regarding the implementation of ERAS protocol components (for the retrospective phase).

5. Sample size

The study utilizes the largest calculated sample size to ensure statistical power across all objectives. For the assessment of the Quality of Recovery (QoR-15), a cross-sectional sample of 115 patients was determined using a single mean estimation formula ($\alpha = 0.05$, $\sigma = 0.82$, $d = 0.15$). For the interventional phase, a power analysis performed via G*Power 3.1.9.4 indicated that a minimum of 54 patients (27 per group) is required to detect an effect size of 0.79 with 80% power at a 0.05 significance level. Consequently, the study aims to enroll at least 115 participants, comprising 68 elective surgery cases and 67 day-surgery cases.

6. Steps to conduct research

Phase 1: Status Assessment and Baseline Evaluation

- Conduct a retrospective cohort study to describe the ERAS implementation status in previous cases via medical records.
- Perform a cross-sectional descriptive study to evaluate the quality of postoperative recovery using the QoR-15 tool and knee function using the LKSS and the cost-effectiveness of treatment using the EQ-5D-5L tool.

Phase 2: Interventional Study and Effectiveness Evaluation

- Intervention Implementation: Apply 06 standardized ERAS measures to the patients
- Evaluate discharge readiness in the recovery unit using the Postanesthetic Discharge Scoring (PADS).
- Monitor and compare outcome variables between elective surgery and day-surgery groups, including recovery quality, complication rates, and cost-effectiveness.
- Collect data at specific intervals: Pre-op (T-1), 1-day post-op (T1), 1 month (T2), 3 months (T3), and 6 months (T4).
- Record the rate of patients requiring readmission within 7 days post-discharge.

7. Research Implementation plan (Gantt chart)

	12/25	4/2026-4/2027	05-06/27	07-12/27
Protocol				
Data collection				
Analyze data and present results				

	12/25	4/2026- 4/2027	05-06/27	07-12/27
Report				

8. References

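### Phase 2 names no primary outcome or time point, and its power statement is attached to no outcome, so the headline result can be chosen after the data are seen

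*Protocol*

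**What the plan says.** The outcomes paragraph of Section 1 reads "Effectiveness will be measured through various outcomes" and names QoR-15 for early recovery and LKSS for knee function. It then adds EQ-5D-5L and a cost-effectiveness analysis by ICER, with no order of importance.

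Objective 2.2 sets three targets side by side: "To evaluate the impact of ERAS interventions on postoperative recovery quality, cost-effectiveness, and the feasibility of implementing a day-surgery protocol".

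Section 6, Phase 2, gives an open list of group comparisons: "Monitor and compare outcome variables between elective surgery and day-surgery groups, including recovery quality, complication rates, and cost-effectiveness". It adds "Record the rate of patients requiring readmission within 7 days post-discharge" and a discharge-readiness score (PADS). The visits are "Collect data at specific intervals: Pre-op (T-1), 1-day post-op (T1), 1 month (T2), 3 months (T3), and 6 months (T4"). It does not say which scale is taken at which visit.

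Section 5 holds two calculations:
- A single-mean estimate for QoR-15 in the cross-sectional part gives 115 patients.
- For the interventional phase, a minimum of 54 patients (27 per group) "is required to detect an effect size of 0.79 with 80% power at a 0.05 significance level". No outcome, visit, standard deviation, test or source is given for this effect size.

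The section opens by saying that the largest calculated size was used so that power is secured for all objectives. In the whole protocol the word primary describes only the type of reconstruction, never an outcome.

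**The concern.** A standardised effect has meaning only for a named variable at a named time. With neither given, a reader cannot judge whether 0.79 is plausible, and the 80% power cannot be set against any result. A single unattributed effect size also cannot support a claim of power for recovery scales, complication rates, an ICER and feasibility together.

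The larger stake is selection. Objective 2.2 asks for a conclusion about impact, and the protocol offers several scales and four postoperative visits from which to draw it. If the scale and visit that carry the conclusion are settled after the data are seen, the 0.05 in Section 5 is not the error rate of that conclusion.

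This belongs in the protocol and is not a detail for an analysis plan. The protocol already commits to a power calculation, and that calculation must have been made for something.

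**Working it through.** **1. Reproduce the plan's own figures.**
- Two-group calculation. Inputs from Section 5: d = 0.79, power 0.80, alpha 0.05, equal groups. A two-sided two-sample t-test (noncentral t) gives 26.15 per group, rounded up to 27, so 2 × 27 = 54. Power at 27 per group is 81.3%. A one-sided test needs only 20.5, rounded up to 21, so the stated figure fits a two-sided test.
- Single-mean calculation. Inputs from Section 5: σ = 0.82, d = 0.15, alpha 0.05. (1.96 × 0.82 / 0.15)² = 114.8, rounded up to 115.

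Both reproduce. Only the second is linked to an outcome (QoR-15), and it concerns estimating one mean, not comparing two groups.

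**2. Illustrate the room for selection.** The protocol fixes neither the number of tests nor their adjustment, so three counts are assumed:
- 3 tests: three scales at one visit, or one overall test per scale.
- 9 tests: QoR-15 at T1 only, plus LKSS and EQ-5D-5L at all four postoperative visits (1 + 2 × 4).
- 12 tests: three scales at four postoperative visits (3 × 4).

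Each is taken as two-sided at 0.05, unadjusted, with no true difference. If the k tests are independent, the chance of at least one false positive is 1 − 0.95^k. For correlated tests, the statistics are taken as normal with one common correlation (an assumed range).

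| Tests | Independent | Corr. 0.3 | Corr. 0.5 | Corr. 0.7 |
|---|---|---|---|---|
| 3 | 14% | 14% | 13% | 11% |
| 9 | 37% | 33% | 27% | 20% |
| 12 | 46% | 40% | 32% | 23% |

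Complications, readmission, PADS and the ICER would come on top of these counts.

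**3. Is the sample too small?** For one continuous outcome, two-sided 0.05 and 80% power, the detectable difference is:
- 68 versus 67 (135 in total): 0.486, about 0.49 SD.
- 115 in total, split 58 and 57: 0.527, about 0.53 SD.

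Both are shown because the same sentence of Section 5 gives at least 115 participants and then two groups that sum to 68 + 67 = 135. Power for d = 0.79 is above 98% in either case. The gap is therefore in what the power statement refers to, not in the number of patients.

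**The case against.** The strongest reply is that the error rates describe a rule the protocol does not contain. The only 0.05 for group comparisons sits inside the sample-size calculation. No test, no visit-by-visit testing and no rule for declaring effectiveness is stated, and tests and multiplicity control are commonly left to an analysis plan, which is not shown here. This stands. A reader might infer that every comparison is tested at 0.05 and that any significant one counts as success. The documents do not say so; they only fail to exclude it.

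The count of tests is also open. QoR-15 is described as a measure of early recovery, which fits poorly with use at 3 and 6 months, so 12 is an upper reading for the three scales. That too stands, and is why the range runs from 3 to 12.

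A third reply is that the sample is ample: at 68 versus 67, even a Bonferroni adjustment over 12 tests would leave 95% power for d = 0.79. This is correct, but it answers a charge of low power, which is not made. It does not say which result is the trial's answer.

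Finally, QoR-15 might be read as the implied primary outcome because it is listed first and appears in Section 5. List order is not a designation, and the sentence in Section 5 that names QoR-15 concerns the cross-sectional estimate. The 0.79 is not linked to it.

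**Conclusion.** The point holds. Phase 2 has no primary outcome or time point, its power statement belongs to no outcome, and the claim of power for all objectives is unsupported. The protocol therefore leaves the headline scale and visit open to choice after the data are seen.

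The possible size is an illustration, not a property of the plan: roughly 11–14%, 20–37% or 23–46% for at least one false positive with 3, 9 or 12 tests. It rests on assumed counts, assumed correlations and no adjustment.

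Two stronger conclusions are not supported. The trial is not shown to be underpowered. Nor would naming a primary outcome by itself bring the rate of false claims to 5%: the protocol describes no randomisation and labels its observational model a cohort, so confounding may remain whatever outcome is chosen.

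**What to change.** In Section 5, before outcome data are seen:

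- Name one primary outcome, one time point and one group contrast for Phase 2. QoR-15 at T1, day-surgery versus elective, is a reasonable candidate, because QoR-15 measures early recovery and recovery quality comes first in objective 2.2. The choice is the investigators'.
- State which outcome and visit the 0.79 refers to and its source. Limit the power claim to that outcome and remove the statement that power covers every objective.
- Declare the remaining scales and visits, complications and readmission secondary, reported with confidence intervals. Report cost-effectiveness and feasibility as separate objectives without a power claim.
- Reconcile the enrolment figure, then restate the detectable effect (about 0.49 SD at 68 versus 67, about 0.53 SD for 115 split about equally).

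The cost is a few sentences, with no change in enrolment or data collection on this account. The one small downside is that a secondary scale cannot be headlined if the primary result is null.

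### An exclusion criterion that can only be judged after surgery limits the Phase 2 comparison to patients who keep attending, and can bias it

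*Protocol*

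**What the plan says.** Protocol section 4 has one list of exclusion criteria for the whole study. One item is "Failure to adhere to the scheduled follow-up visits". The item after it is confined to one phase: "Incomplete medical records regarding the implementation of ERAS protocol components (for the retrospective phase"). The follow-up item has no such limit.

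The only visit schedule is in section 6, under Phase 2: "Pre-op (T-1), 1-day post-op (T1), 1 month (T2), 3 months (T3), and 6 months (T4"). The same list of steps says "Record the rate of patients requiring readmission within 7 days post-discharge", and also that the investigators will "compare outcome variables between elective surgery and day-surgery groups, including recovery quality, complication rates, and cost-effectiveness". Section 1 describes QoR-15 as measuring "the quality of early recovery via the QoR-15 score".

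The protocol does not say what happens to data already collected from a patient who later meets the criterion. It names no analysis set that would keep such a patient.

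**The concern.** An eligibility criterion should be decidable before treatment. This one cannot be: whether a patient attends at 1, 3 and 6 months is known only after consent, surgery and the day-1 assessment. As written, membership of the study population depends on behaviour after treatment.

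The outcomes most relevant to objective 2.2 (early recovery and the feasibility of day surgery) arise early. A patient with a poor day-1 recovery or an early complication who then misses the 3-month visit meets an exclusion criterion. On the plain meaning of exclusion, that patient leaves both numerator and denominator.

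Attendance may well be related to outcome, and in either direction. A patient may stop coming because a complication is being treated elsewhere, or because recovery went very well. Any such relation distorts the completers' means and rates. If it, or the amount of loss, differs between the elective and day-surgery groups, the comparison is distorted too. Enrolling more patients does not cure this.

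**Working it through.** **1. When can the criterion be judged?** The post-operative visits are T1 (day 1), T2 (1 month), T3 (3 months) and T4 (6 months). Adherence to the full schedule is settled only at T4, and the first visit after T1 that can be missed is T2. Day-1 data therefore exist before a later visit can be missed.

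**2. Which phase does it govern?** The neighbouring item is restricted to the retrospective phase and this one is not. Scheduled visits appear only under Phase 2. The criterion therefore reaches the group comparison.

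**3. The plan's own sample sizes (section 5).**
- Single mean, from the "single mean estimation formula ($\alpha = 0.05$, $\sigma = 0.82$, $d = 0.15"): n = (1.96 × 0.82 / 0.15)² = 114.80, rounded up to 115. This reproduces.
- Two groups, effect size 0.79, two-sided alpha 0.05, t test: power is 0.798 at 26 per group and 0.813 at 27 per group. The stated 27 per group (54 in total) reproduces.
- Planned groups of 68 and 67 (68 + 67 = 135): power for 0.79 is 0.995. After 10%, 20% or 30% loss it is 0.991, 0.982 or 0.968.

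Loss of power for the group comparison is therefore not the problem. The issue is selection.

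**4. Size of the possible bias.** The protocol gives no attendance rate, event rate or outcome gap, so all inputs in this step are assumptions. Let f be the fraction of non-attenders. At f = 0.15, about 20 of 135 patients are removed (0.15 × 135 = 20.25), leaving 115.

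*A mean.* If non-attenders score k SD worse than attenders, the completers' mean is too high by f × k.
- k = +1 (worse): 0.15 × 1 = +0.15 SD.
- k = 0 (unrelated): 0.
- k = -1 (better): 0.15 × (-1) = -0.15 SD.

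*A group difference.* The shift is f₁k₁ - f₀k₀.
- Loss of 20% and 5%, same k in both groups: (0.20 - 0.05) × k = 0.15k. For k from -1 to +1 this runs from -0.15 to +0.15 SD.
- Against the stated effect size: 0.15 / 0.79 = 19%.
- Equal loss and equal k: 0.
- Equal loss of 15%, with a 1 SD gap in one group only: 0.15 × 1 - 0.15 × 0 = 0.15 SD.

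*An event rate.* If non-attenders have RR times the attenders' risk, completers' rate / true rate = 1 / (f × RR + 1 - f). At f = 0.15 and a true rate of 10%:

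| RR | Ratio | Rate reported |
|---|---|---|
| 0.5 | 1 / 0.925 = 1.081 | 10.8% |
| 1 | 1 / 1.00 = 1 | 10.0% |
| 2 | 1 / 1.15 = 0.870 | 8.7% |
| 3 | 1 / 1.30 = 0.769 | 7.7% |

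Over f = 0.10 to 0.30, RR of 2 to 3 gives rates 9% to 38% too low in relative terms (1 / 1.10 = 0.909; 1 / 1.60 = 0.625). RR of 0.5 gives rates 5% to 18% too high (1 / 0.95 = 1.053; 1 / 0.85 = 1.176).

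**The case against.** The strongest reply is that the line may be a loosely worded withdrawal rule, and that analysis sets and missing-data handling belong in a SAP, which may exist. That would answer a complaint that methods are missing. It does not answer this point: the protocol itself states who is excluded, and a SAP could retain these patients only by departing from that rule.

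Several stronger readings are tempting, and the protocol does not support them.

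- A reader might infer that collected data will certainly be deleted. The protocol does not say so. Deletion is the natural consequence of exclusion, but it is a consequence and not a stated step.
- A reader might infer that 7-day readmission is always known before a visit is missed. The schedule goes from day 1 to 1 month with no 7-day contact, and the protocol does not say how readmission is ascertained. If it is asked at T2, a patient who misses T2 has no status to discard.
- A reader might infer that complications and readmissions will be understated. The direction is unknown, since patients who recover well may also stop attending.
- A reader might infer that day-surgery patients will be lost more often. Section 6 gives one schedule with no difference by group, so differential loss is possible but not shown.

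It also stands that no stated sample size changes, and that the bias is zero if attendance is unrelated to outcome.

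**Conclusion.** The criterion is wrong as written. It is listed as an eligibility rule but depends on behaviour up to 6 months after treatment, and it applies to the Phase 2 comparison. Applied literally, it gives a completers-only comparison and may discard observed outcomes, including any readmission already known.

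That conclusion rests on the text alone. The size does not: the protocol fixes neither magnitude nor sign. Under the assumed 15% non-attendance and a gap of up to 1 SD either way, a mean moves by at most 0.15 SD. A 15-point difference in loss, with the same gap in both groups, moves the group difference by at most 0.15 SD, or about 19% of 0.79. Larger loss, or gaps running in opposite directions in the two groups, would give more; no relation between attendance and outcome gives zero. The criterion brings no gain in validity in any of these cases, and removing patients also removes the information needed to tell which case holds.

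**What to change.** Delete this criterion from section 4, or replace it with one judged at enrolment, for example: unable, at enrolment, to attend or be reached for 6 months.

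State in the protocol that:
- every enrolled patient who had surgery stays in the analysis by group, with all observed data used;
- missed visits are treated as missing data, not as grounds for exclusion;
- readmission and complication rates are based on all operated patients, with unknown status reported as unknown and not counted as no event;
- loss to follow-up is reported by group.

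The choice of model for the incomplete data can be left to the SAP. No stated sample size changes. The cost is one reworded criterion, a little more analysis work and some missing values to handle. The change should be made before any exclusions are applied, because discarded patients may not be recoverable later.

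### Excluding retrospective records with incomplete ERAS documentation selects patients on the variable Objective 2.1 describes, so the compliance estimate covers only well-documented cases and is likely, though not certain, to be too high.

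*Protocol*

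**What the plan says.** Protocol section 2, Objective 2.1, is "To describe the current status of ERAS program implementation among patients undergoing arthroscopic anterior cruciate ligament reconstruction (ACLR") at the centre. Section 1 describes the same task as a matter of compliance: "This study aims to evaluate the current compliance with ERAS and the effectiveness of fully implementing these protocols".

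The method is in section 6, Phase 1: "Conduct a retrospective cohort study to describe the ERAS implementation status in previous cases via medical records". No other source is named for whether a component was delivered.

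Section 4 lists among the exclusion criteria: "Incomplete medical records regarding the implementation of ERAS protocol components (for the retrospective phase"). The protocol does not define when a record is incomplete. It does not say whether a record that is silent on a component means not delivered or unknown, and it does not provide for counting or describing the excluded records. Section 1 lists six core ERAS measures for the intervention. The components to be audited retrospectively are not listed separately.

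**The concern.** What is to be described is whether each ERAS component was carried out, and the only evidence is the chart. A rule that drops charts according to how fully they record ERAS delivery therefore selects on the outcome. Objective 2.1 concerns patients having the operation at this centre, but the rule yields a figure for the subset whose ERAS care was well charted.

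Selection of this kind does no harm only if compliance is the same in included and excluded charts, and there is reason to doubt that. Measures such as counselling, the preoperative drink or rehabilitation in the recovery unit tend to leave an entry when they are done and none when they are not. If so, the excluded charts carry lower compliance and the reported figure is too high.

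There is also a loss of information. If one missing entry makes a record incomplete, the patient's usable entries on every other component go with it.

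At stake is the first of the two objectives: the description of how far current practice falls short of full implementation.

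**Working it through.** **What the protocol supplies.** No compliance rate, no share of incomplete records and no sample size for the retrospective estimate. The nearest stated figures are the two sample sizes in section 5, and both reproduce:

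- "a cross-sectional sample of 115 patients was determined using a single mean estimation formula": n = (1.96 × 0.82 / 0.15)² = 114.8, rounded up to 115.
- "a minimum of 54 patients (27 per group) is required to detect an effect size of 0.79 with 80% power at a 0.05 significance level": a two-sided two-sample t-test gives 26.1, so 27 per group and 54 in all.

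Neither bears on this point. Everything below rests on assumed inputs.

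**Bias formula.** Let m be the share of records excluded, p_c the compliance in complete records and p_i the compliance in excluded records. True compliance is (1 − m)·p_c + m·p_i, while the plan reports p_c. The bias is therefore m·(p_c − p_i). It is positive when excluded patients received the component less often, zero when p_i = p_c, and negative when they received it more often. With p_c = 80% and m = 20%:

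- p_i = 0%: 0.20 × (0.80 − 0) = +16 points
- p_i = 50%: 0.20 × (0.80 − 0.50) = +6 points
- p_i = 80%: 0
- p_i = 100%: 0.20 × (0.80 − 1.00) = −4 points

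**Case A, extreme bound: every incomplete record lacks the same component.** Nothing is known about that component in the excluded records. The lower bound (not documented = not done) is (1 − m)·p_c and the upper bound (not documented = done) is (1 − m)·p_c + m. At m = 20% these are 0.80 × 0.80 = 64% and 0.64 + 0.20 = 84%.

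**Case B, even spread: each incomplete record lacks exactly one of six components.** Assume also that the six core measures are those audited and that documented compliance is 80% in all records, complete or not. Each component is then undocumented in m/6 of patients; at m = 20% this is 3.33%. The lower bound is (1 − m/6) × 0.80 = 0.9667 × 0.80 = 77.3%, and the upper bound is 0.773 + 0.033 = 80.7%.

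| Incomplete records (m) | Plan reports | Case A | Case B |
|---|---|---|---|
| 10% | 80% | 72% to 82% | 78.7% to 80.3% |
| 20% | 80% | 64% to 84% | 77.3% to 80.7% |
| 30% | 80% | 56% to 86% | 76.0% to 81.0% |

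**Data discarded.** In Case B at m = 20%, 100 patients yield 80 × 6 + 20 × 5 = 580 documented entries. The rule drops 20 × 5 = 100 of them, or 17%, although each is valid.

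**How quickly exclusions build up.** If one gap makes a record incomplete and gaps are independent across six components, 3% undocumented per component excludes 1 − 0.97⁶ = 17% of patients, and 5% excludes 1 − 0.95⁶ = 26%.

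**The case against.** The strongest reply is that the direction and size are not in the document. The protocol says nothing about charting practice. The premise that undelivered care goes unrecorded is reasoning about records in general, and the ranges above include values on the other side of 80%. That stands: a reader might infer that upward bias is established, but the text supports only that it is likely.

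A second reply is that 64% to 84% overstates the uncertainty. A reader might take it as the plausible range, yet it requires every incomplete chart to be silent on the same item. If gaps are scattered, most excluded patients have a known value for any given component and the possible overstatement at 20% incomplete is under 3 points. That also stands, provided documented compliance is the same in incomplete charts; if it is lower there, the overstatement is larger.

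Third, a reader might infer that an inflated baseline shrinks the apparent gain in Phase 2. The protocol does not support this. Section 6 compares elective with day-surgery groups on recovery quality, complication rates and cost-effectiveness, and no before/after comparison of compliance is specified.

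Fourth, incomplete is undefined and might mean an unusable record rather than one missing entry. On that reading fewer patients would be lost, but the text does not say so, and the criterion is tied expressly to ERAS components.

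None of this removes the selection itself. It is fixed as an eligibility rule in the protocol, nothing elsewhere in the protocol offsets it, and an analysis plan cannot recover charts excluded before abstraction.

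**Conclusion.** The point holds in a limited form. The exclusion conditions on the variable that Objective 2.1 is meant to describe, so the compliance estimate applies to well-documented cases only, and valid entries on other components are discarded. Upward bias is the likely direction, on the assumption that an unrecorded component is more often one not delivered; zero or downward bias cannot be ruled out.

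The size is unknown. With an assumed 80% compliance in complete records and 20% of records incomplete, the reported figure could be too high by anything from under 3 points (scattered gaps, one per chart, equal documented compliance) to 16 points (all gaps on one component, none delivered). It could also be too low by about 1 to 4 points in the corresponding opposite cases.

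The effect is confined to a descriptive objective, and nothing is claimed about the Phase 2 elective versus day-surgery comparison. The change should be made because the rule compromises a named objective and is easily corrected before abstraction.

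**What to change.** - Delete this criterion for the retrospective phase and keep all eligible consecutive cases. Exclude a case only if the whole record cannot be retrieved, and report how many were excluded for that reason.
- Code each ERAS component in each record as done, not done or not documented.
- Report compliance per component as the documented-only figure, with both bounds beside it: not documented counted as not done, and not documented counted as done. Neither bound need be named the main result, since counting every silence as non-delivery would understate compliance where care was given but not charted.

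The cost is slightly more chart abstraction, one more coding category and extra columns in the compliance table. The compliance result will be wider and possibly less favourable. No new patients are needed and clinical care is not affected.

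### Section 5 claims power for every objective, but 115 is a precision size for one mean, the only power calculation names no outcome, and 115 does not match 68 + 67 = 135

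*Protocol*

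**What the plan says.** Section 5 opens with the claim "The study utilizes the largest calculated sample size to ensure statistical power across all objectives". Two calculations follow.

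- For QoR-15, "a cross-sectional sample of 115 patients was determined using a single mean estimation formula", with alpha 0.05, SD 0.82 and d 0.15.
- For the interventional phase, "a minimum of 54 patients (27 per group) is required" "to detect an effect size of 0.79 with 80% power at a 0.05 significance level". The outcome, the test and the sidedness are not given.

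The section concludes that "the study aims to enroll at least 115 participants, comprising 68 elective surgery cases and 67 day-surgery cases".

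Objective 2.2 reads, in part, "To evaluate the impact of ERAS interventions on postoperative recovery quality, cost-effectiveness, and the feasibility of implementing a day-surgery protocol". Section 6 adds that complication rates will be compared between the elective and day-surgery groups, and that 7-day readmission will be recorded. Section 1 expects the study to show that strict ERAS adherence, among other things, "reduces hospital-acquired infections, optimizes operating room productivity, and lessens the financial burden on both patients and the healthcare system". The protocol gives no event rate for any of these outcomes.

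**The concern.** Taking the largest of several sample sizes secures power for every objective only if each objective has its own power calculation. Here the largest figure is not a power calculation, and most of what objective 2.2 covers has no calculation of any kind. The protocol therefore states a property that it has not shown.

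This matters most for safety after same-day discharge. If the protocol promises power throughout, a reader could take a non-significant difference in complications as evidence that the two pathways are equally safe, when the data may be compatible with a sizeable difference. Likewise, a real reduction in hospital-acquired infection, which section 1 expects to show, might well go undetected. The recruitment target is also unclear, because the stated total and the stated groups disagree.

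**Working it through.** **Inputs from section 5:** SD 0.82, d 0.15 and alpha 0.05 for the single mean; effect size 0.79, power 80% and alpha 0.05 for the comparison; groups of 68 and 67.

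**1. The plan's 115.** n = (z × SD / d)² = (1.96 × 0.82 / 0.15)² = 114.8, rounded up to 115. It reproduces. The formula fixes the half-width of a 95% confidence interval. It contains neither a power term nor a difference between groups.

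**2. The plan's 27 per group.** A two-sided two-sample t-test (noncentral t) with standardised difference 0.79 and alpha 0.05 gives 81.3% power at 27 per group and 79.8% at 26. So 27 reproduces, if the test is a two-sided t-test. A one-sided test would need only 21.

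**3. The enrolment total.** 68 + 67 = 135, which is 20 more than 115. The wording allows more than 115, but 115 cannot consist of 68 and 67.

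**4. What 68/67 delivers for a continuous outcome** (two-sided 5%). Power for an effect of 0.79 is 99.5%. The effect detectable with 80% power is 0.49 SD.

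**5. Precision of a mean at SD 0.82** (half-width = 1.96 × 0.82 / √n):

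| n | Half-width |
|---|---|
| 115 | 0.150 |
| 135 (both groups pooled) | 0.138 |
| 68 (elective) | 0.195 |
| 67 (day surgery) | 0.196 |

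The pooled mean meets 0.15. A mean within either pathway does not: 0.195 / 0.15 = 1.30, so the margin is about 30% wider.

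**6. Event outcomes at 68/67.** The rates are assumptions, because the protocol gives none. The test is a two-sided Fisher exact test at 5%, with power by full enumeration.

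| Assumed rates | Power |
|---|---|
| 5% vs 1% | 7% |
| 10% vs 5% | 11% |
| 10% vs 3% | 24% |
| 20% vs 10% | 30% |
| 20% vs 5% | 71% |
| 30% vs 10% | 81% |

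**7. A group with no events.** The upper limit of the two-sided exact 95% interval for 0 of 67 is 1 − 0.025^(1/67) = 5.4%. Against 0 of 67, the elective group would need 6 of 68 events for p < 0.05 (p = 0.028); 5 of 68 gives p = 0.058.

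**8. Calculations against what is promised.** Of the items in objective 2.2, recovery quality may be what the 0.79 refers to, but the protocol does not say so. Cost-effectiveness and feasibility have no calculation. Nor do complications, infections or readmission. Infections could fall under the complication rates in section 6; operating-room productivity has no listed measure.

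**The case against.** The case for the plan is substantial in several respects.

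- **The study is not too small for what it calculated.** Power of 99.5% for the 0.79 effect is ample. This stands. A reader might infer that the trial is underpowered throughout, but the figures do not support that.
- **The 0.15 margin is not lost.** A reader might infer that 115 is divided between two groups, so that no population gets the stated precision. But the groups sum to 135, section 5 ties 0.15 to one cross-sectional mean, and it promises no per-group margin. Pooled over 135 the margin is 0.138. The wider margin applies only if per-group means are reported.
- **Infections, complications and readmission are not numbered objectives.** This is correct. Readmission is only to be recorded, and infection reduction is an expectation in the summary. The power claim fails on objective 2.2 alone, through cost-effectiveness and feasibility, without any assumed event rate.
- **Low event power depends on assumed rates and on the test.** This also stands. Complications are not defined and may include common events, for which power can reach about 70 to 80%. Fisher's test is conservative: an uncorrected chi-square gives 25% rather than 7% for 5% versus 1%, and 36% rather than 24% for 10% versus 3%. Power is still low in those cases, but it would be too strong to say that the study has almost no power for any event.
- **Unpowered secondary outcomes are ordinary, and their interpretation often belongs in the SAP.** This is true, and nothing in the protocol says that non-significance will be read as safety. It does not rescue a sentence in the protocol that claims power for everything.

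**Conclusion.** Wrong as written; moderate severity. The sentence claims power across all objectives. The figure behind it is a precision size, the single power calculation is attached to no named outcome, and two of the three elements of objective 2.2 have no calculation. The enrolment sentence also contradicts itself by 20 patients.

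The conclusion on objective 2.2 needs no outside assumption. The 99.5% and 0.49 SD figures assume a two-sided t-test with complete data on 68 and 67 patients. The event figures rest on assumed rates and show only that power is low unless events are common and the contrast is large. The severity is not higher because the one calculated comparison is well covered and the repair is to the text alone.

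A reader might take QoR-15 at T1 as the powered comparison. The protocol does not link 0.79 to that outcome or time point, so the sponsor has to state it.

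**What to change.** 1. In section 5, replace the opening claim with a power statement limited to the outcome and time point behind the 0.79 effect size, to be named by the sponsor, with the test and its sidedness.
2. Label 115 as a precision size for the pooled cross-sectional QoR-15 mean. Give the scale to which SD 0.82 and d 0.15 refer, and state the wider margin of about 0.20 if per-group means are reported.
3. Reconcile the total of 115 with 68 + 67 = 135.
4. State that complications, infections, readmission, feasibility and cost-effectiveness are estimated with 95% confidence intervals and are not powered, and that a non-significant difference will not be read as equivalence.
5. In section 1, soften the expected demonstration of fewer infections and better operating-room productivity. If productivity stays, list a measure for it.

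The cost is wording in sections 1 and 5, plus one line in section 6 if productivity is kept. No extra patients are needed. The stated claims become less favourable to the study.
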